### **Estimation of sample size**

Our recent study showed that CAT treatment for 8 weeks produced a  $2.3 \pm 2.8$  (SD) score greater improvement than control (minimum acupuncture stimulation, MAS) on MoCA in patients with poststroke cognitive impairment. One similar trial has reported that acupuncture treatment alone for 3 months yielded a  $1.9 \pm 4.1$  greater improvement than nimodipine, a commonly used anti-hypertension drug, on MoCA in patients with poststroke cognitive impairment. Based on these two trials, we expect that CAT could yield an average  $2.1$  [ $(2.3+1.9)/2 = 2.1$ ] score greater improvement on MoCA than routine care, with an average standard deviation (SD) equal to a 1.7-fold of mean difference [ $(2.8/2.3 + 4.1/1.9)/2 = 1.7$ ], i.e.,  $SD = 1.7 \times 2.1 = 3.6$ . The following formula is then used to further calculate the sample size:

$$n = \frac{2}{(M/SD)^2} \times C_{p,\text{power}}$$

where  $n$  is the number of subjects required in each arm and  $M$  is the mean difference that is equal to 2.1.  $SD$  is the standard deviation that is 3.6.  $C_{p,\text{power}}$  is equal to 7.9 when the two-tailed level of  $\alpha$  and power ( $1-\beta$ ) are set at 0.05 and 80%, respectively. It requires 62 subjects per arm, with an assumed dropout rate of 25%. We propose to recruit a total of 248 subjects ( $n = 62$  per arm for 4 arms).

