## **Treatment procedure**

(a) Routine care: All participants in the four groups will continue their current routine care and medications as usual. These routine cares will serve as covariates included in outcome analysis.

(b) CAT regimen: Subjects assigned to the CAT group will receive CAT treatment in addition to routine care. CAT will be conducted for 2 sessions per week for 12 consecutive weeks, a total of 24 treatment sessions. Registered Chinese medicine practitioners (CMPs) with a master's degree or above and with at least 5 years of acupuncture experience will be responsible for acupuncture treatment. A brief introduction to acupuncture procedures will be given by a CMP during the first visit. Details of selected acupoints are illustrated and summarized in [Figure 2](#) and [Table 1](#).

The acupuncture treatments will be conducted at the subjects' corresponding care homes. Each subject will receive a maximum of 26 needles per treatment session, adjusted by their tolerance, in a supine position. The following 14 body acupoints with only manual stimulation will be used: Shenmen (HT7, 神門), Hegu (LI4, 合谷), Waiguan (TH5, 外關), Zusani (ST36, 足三里), Fenglong (ST40, 豐隆) and Sanyinjiao (SP6, 三陰交) on both sides, and Zhongwan (CV12, 中脘) and Guanyuan (CV4, 關元) in the midline. Meanwhile, electrical stimulation will be conducted on six pairs of frontal acupoints with positive (+) and negative (-) electrode cord connections as follows: Baihui (GV20, 百會) and Yintang (EX-HN3, 印堂), left Sishencong (EX-HN1, 四神聰) and Toulinqi (GB15, 頭臨泣), right Sishencong (EX-HN1, 四神聰) and Toulinqi (GB15, 頭臨泣), bilateral Shuaigu (GB8, 率谷), bilateral Taiyang (EX-HN5, 太陽), and bilateral Touwei (ST8, 頭維).

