### **Assessment**

(a) Primary outcome: The primary outcome will be evaluated by the mean change of the Montreal Cognitive Assessment (MoCA) score between baseline and endpoint. The MoCA test assesses seven domains of cognitive function, including visuospatial, naming, attention, language, abstraction, recall, and orientation domains, for a total possible score of 30 points. It has been well established for the detection of MCI, with sensitivity for detecting MCI of 90% compared to 18% for the Mini-Mental State Examination (MMSE), and the evaluation of the severity of cognitive impairment. A score of 25 points or less is indicative of cognitive impairment, but the score needs to be adjusted for age and education. We have applied MoCA in the two previous studies.

(b) Secondary outcomes: The secondary outcomes will include the Digit span test for attentional function, short-term memory, and working memory, the Modified Barthel Index (MBI) for functional independence, the Visual Analogue Scale (VAS) for pain, the 15-item Geriatric Depression Scale (GDS-15) for depression, and the Insomnia Severity Index (ISI) for insomnia.

Digit Span is a measure of working and short-term memory, and is evaluated in two formats, Forward Digit Span and Reverse Digit Span, with a total possible score of 14 points, respectively. The Digit span test is a simple test to further evaluate subjects' attentional function, short-term memory, and working memory.

MBI is a validated outcome measure to evaluate the functional status of patients. MBI consists of 10 items, i.e., feeding, bathing, grooming, dressing, bowel control, bladder control, toileting, chair transfer, ambulation, and stair climbing, to score with a five-step scoring system. MBI score ranges from 10 to 50, with a higher score indicating a higher level of independence. VAS is a simple instrument to measure subjective experience in pain. A horizontal line that represents the severity of symptoms from 0, no pain, to 10, very severe pain, is shown, and the patient should mark the point on the line that reflects the subject's perception of the current state. Functional independence and pain are measured, as previous studies have confirmed the benefits of acupressure and acupuncture in improving disability and pain.

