Our recent study showed that CAT treatment for 8 weeks produced a 2.3 ± 2.8 (SD) score greater improvement than control (minimum acupuncture stimulation, MAS) on MoCA in patients with poststroke cognitive impairment.¹³ One similar trial has reported that acupuncture treatment alone for 3 months yielded a 1.9 ± 4.1 greater improvement than nimodipine, a commonly used anti-hypertension drug, on MoCA in patients with poststroke cognitive impairment.¹⁴ Based on these two trials, we expect that CAT could yield an average 2.1 [$(2.3+1.9)/2 = 2.1$] score greater improvement on MoCA than routine care, with an average standard deviation (SD) equal to a 1.7-fold of mean difference [$(2.8/2.3 + 4.1/1.9)/2 = 1.7$], i.e., $SD = 1.7 \times 2.1 = 3.6$. The following formula is then used to further calculate the sample size:

$$n = \frac{2}{(M/SD)^2} \times C_{p,\text{power}}$$

where n is the number of subjects required in each arm and M is the mean difference that is equal to 2.1. SD is the standard deviation that is 3.6. $C_{p,\text{power}}$ is equal to 7.9 when the two-tailed level of α and power ($1-\beta$) are set at 0.05 and 80%, respectively. It requires 62 subjects per arm, with an assumed dropout rate of 25%. We propose to recruit a total of 248 subjects ($n = 62$ per arm for 4 arms).

Data processing and analysis

General principles

One biostatistician who is blinded to interventions will be responsible for statistical analysis. The analysis will be carried out on the intention-to-treat (ITT) population. For all primary and secondary outcomes, two-tailed P-values will be reported in addition to confidence intervals. The nominal level of statistical significance (α) will be 5%. The analysis and reporting of the results will follow the Consolidated Standards of Reporting Trials (CONSORT) guidelines.

Analysis software

All analyses will be performed using R Studio version 4.0.0 or later.

Analysis Populations

All analyses will be carried out on the intention-to-treat (ITT) population, for which participants have been randomized, completed the baseline assessment regardless of protocol compliance.¹⁵ The flow of patients throughout the trial will be shown using a CONSORT diagram (Figure 1).

Demographic characteristics and baseline comparisons

Baseline comparisons will be tabulated for the following variables (Proposed Table 1):

- (a) Age
- (b) Gender (Categories: male / female)

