- (c) Marital status (Categories: married or living with partner / single, separated, divorced, or widowed)
- (d) Education level (Categories: uneducated / primary or below / lower secondary / upper secondary / university or above)
- (e) Past occupation (Categories: managers and administrators / professional and associate professional / skilled and semi-skilled worker / unskilled worker / housework / others)
- (f) Type of cognitive impairment (Categories: Alzheimer's disease / vascular dementia / others)
- (g) Past medical history (Categories: cardiometabolic disease / malignant neoplasm / stroke / Parkinson's disease / psychotic disorder / affective disorder)
- (h) Current medication (Categories: cholinesterase inhibitors / glutamate regulators / antidepressants / antipsychotics / hypnotics)

- (i) Baseline MoCA score
- (j) Baseline DSF and DSR scores
- (k) Baseline MBI score
- (l) Baseline VAS score
- (m) Baseline GDS-15 score
- (n) Baseline ISI score

Continuous variables will be presented using mean with standard deviation (SD). One-way analysis of variance (one-way ANOVA) will be used to detect differences in continuous baseline variables.

Categorical variables will be presented by counts with percentages. Percentages will be calculated according to the number of patients for whom data are available. Categorical variables will be analyzed using the Chi-square test or Fisher's exact test.

Discontinuation will be summarized by counts with percentages. Chi-square test or Fisher's exact test will be used to detect differences between the four groups.

Primary outcome

A linear mixed-effect model will be applied to compare the primary outcome (changes in total MoCA score from baseline), with time (baseline, week 6, and week 12) and group (CAT, CAE, CAT+CAE, and routine care) as categorical fixed factors and random intercepts within a scaled identity covariance matrix. Gender, age, baseline MoCA score, and baseline medication will serve as covariates. Pairwise comparisons will be further carried out to examine between-group differences. Two-tailed P-values will be reported in addition to confidence intervals ([Proposed Tables 2 and 3](#)).

Subgroup analysis will be further conducted to compare outcomes to detect whether these subgroup factors are associated with outcomes. The following subgroups include:

- (a) Age (<85 years and \geq 85 years);
- (b) Gender (male and female); and

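### Education is collected but left out of the MoCA model without a reason; adding it as one ordinal covariate is a cheap, small gain in precision

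*Protocol*

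**What the plan says.** The protocol (Assessment, item (a)) defines the endpoint: "The primary outcome will be evaluated by the mean change of the Montreal Cognitive Assessment (MoCA) score between baseline and endpoint". The same paragraph gives the scale's maximum as 30 points, takes 25 points as the upper limit for impairment, and qualifies that reading: "but the score needs to be adjusted for age and education".

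The covariates are listed in the protocol (Data processing and analysis) and in the SAP (Primary outcome, repeated under Secondary outcomes): "Gender, age, baseline MoCA score, and baseline medication will serve as covariates". Under Treatment procedure the protocol adds routine care: "These routine cares will serve as covariates included in outcome analysis". Education appears in neither list and is not a subgroup factor.

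Education is nevertheless recorded. The SAP (Demographic characteristics and baseline comparisons, item (d)) lists "Education level (Categories: uneducated / primary or below / lower secondary / upper secondary / university or above". Its only stated use is the baseline comparison in proposed Table 1, where it is tested across the four arms. The randomisation sections describe blocks of 4, 8 and 12 and state no stratification.

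**The concern.** The protocol names two participant characteristics as relevant to a MoCA score. One is in the model and the other is not, although it is on file for the baseline table. Age and education are treated differently and no reason is given.

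What is at stake is precision. Baseline MoCA, which is in the model, carries much of any education effect on the level of the score, but not all of it. Two people with the same observed baseline score and different schooling tend to regress towards different means at the next test. Education can therefore predict change given baseline, and whatever it predicts now stays in the residual of the primary endpoint. The same could apply to Digit Span, though the documents make no such remark about that test.

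**Working it through.** **The plan's own figure.** With a difference of 2.1, an SD of 3.6 and a multiplier of 7.9 (protocol, Estimation of sample size), n = 2/(2.1/3.6)² × 7.9 = 46.4 per arm. Then 46.4/(1 - 0.25) = 61.9, so 62 per arm and 248 in total. The figure reproduces. The formula has no covariate term, so it does not depend on whether education is in the model. Expected completers are 62 × 0.75 = 46.5 per arm, or 186 in total.

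**A fixed correction cancels.** If a participant's score is corrected by k points for education at every visit, (end + k) - (base + k) = end - base. Apart from any cap at 30, change is the same. Neither document says whether the raw or the corrected total is analysed. For change this hardly matters if one rule is used at all visits.

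**What does not cancel.** Let education explain a share s of the variance V of MoCA level, with the same effect on level at both visits, and let ρ be the retest correlation within an education level.

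- Variance of change = 2V(1 - s)(1 - ρ)
- If education moves level by b, its coefficient for change given baseline is b(1 - ρ)
- Share of the remaining variance of change explained by education once baseline MoCA is in the model: R² = s(1 - ρ) / [s(1 - ρ) + 1 + ρ]

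Inputs: SD of change 3.6, from the sample size section; level SD 5, so V = 25 (assumption); s from 0% to 30% (assumption). Then 1 - ρ = 3.6² / [50(1 - s)].

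**Degrees of freedom.** The existing covariates use about 8: gender, age and baseline MoCA one each, and the SAP's five medication classes five. With 186 completers and four arms, adding q parameters multiplies the variance of a treatment contrast by about 173/(173 - q), where 173 = 186 - 4 - 8 - 1. The SE ratio, with education against without, is √[(1 - R²) × 173/(173 - q)].

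| s | 1 - ρ | R² | SE ratio, one ordinal term (q = 1) | SE ratio, five categories (q = 4) |
|---|---|---|---|---|
| 0% | 0.259 | 0 | 1.003 | 1.012 |
| 10% | 0.288 | 1.7% | 0.995 | 1.003 |
| 20% | 0.324 | 3.7% | 0.984 | 0.993 |
| 30% | 0.370 | 6.4% | 0.970 | 0.979 |

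Example, s = 30%, q = 1: R² = 0.3 × 0.370/(0.3 × 0.370 + 1.630) = 0.064; √(0.936 × 173/172) = 0.970.

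Level SDs of 4 to 6 with s from 10% to 30% give R² from 1.1% to 10.9%, so the result depends on this assumption too.

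**Check by simulation.** In a four-arm ANCOVA with 46 completers per arm, level SD 5 and a true effect of 2.1 in one arm, power at s = 10%, 20% and 30% was 83.9%, 84.0% and 84.1% without education. It was 84.5%, 85.1% and 86.2% with one ordinal term, and 83.7%, 84.5% and 85.7% with five categories. The ordinal term gains 0.6 to 2.1 points of power. Five categories give less, and nothing at the low end.

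**The case against.** The strongest reply is that the plan needs no change. Several parts of it stand.

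- A reader might infer that the protocol demands an education adjustment which its own model then fails to make. The text does not support that. The remark qualifies the 25-point cut-off for impairment, which the trial does not use: eligibility rests on diagnosis and Global Deterioration Scale stage, and the endpoint is change.
- A reader might infer that the treatment estimates are biased. They are not. Allocation is randomised, and the confidence intervals already allow for chance imbalance. In a two-arm simulation (47 per arm, ANCOVA with baseline MoCA), type I error without and with education was 4.0% and 4.0%, or 4.3% and 4.4% when education also affected change. The estimate of a true 2.1 stayed between 2.07 and 2.10.
- The model does not adjust for age alone. It also has gender, baseline MoCA and baseline medication.
- The gain is easy to overstate by counting all 248 participants or by ignoring degrees of freedom. With five categories, power in the two-arm simulation was no better: 83.2% without against 81.6% with, and 81.4% against 80.0%. That setting has only 94 participants and uses the costlier coding, so it argues against five categories more than against a single term.
- Two people with the same baseline score have the same number of points left on the scale. The case therefore rests on regression towards different means, not on room to gain.

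It can also be said that proposed Table 1 will show any imbalance in education. That is true, but the SAP gives no rule for acting on one. A covariate added after seeing that table would be data-driven; a prespecified one is not.

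**Conclusion.** The point holds as a cheap improvement. Education is already on file, the protocol itself treats it as relevant to the MoCA score, and it can still predict change once baseline MoCA is in the model. Leaving it out gives up a little precision and does not threaten validity.

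With about 186 completers, one ordinal term changes the standard error by about +0.3% if education is unrelated to MoCA level, and by about -3% if it explains 30% of the variance in level. This rests on an assumed level SD of 5, the plan's SD of change of 3.6, an education effect on level that is linear and equal at both visits, and an ANCOVA on change as a stand-in for the planned mixed model. Partial data from participants who drop out could shift the figures slightly. The sample size of 62 per arm is unaffected.

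**What to change.** In the protocol (Data processing and analysis) and the SAP (Primary outcome), extend the covariates of the MoCA model to gender, age, education level, baseline MoCA score and baseline medication. State that education enters as one ordinal term scored across the five existing levels, not as five categories. The Digit Span models under Secondary outcomes may take the same term. The documents give no reason to add it to the MBI, VAS, GDS or ISI models.

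The cost is one phrase in each document, one degree of freedom, an assumed linear trend across levels, and a negligible loss of precision if education turns out to be unrelated to MoCA. No new data are needed. The change should be made before the analyst sees outcome data by arm.

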The GDS-15 consists of 15 questions in which subjects are asked to respond by answering yes or no in reference to how they felt over the past week. Of the 15 items, 5 items (question numbers 1, 5, 7, 11, 13) indicate depression when answered negatively, while the rest (question numbers 2, 3, 4, 6, 8, 9, 10, 12, 14, 15) indicate the presence of depression when answered positively. The GDS-15 score is interpreted as follows: normal (0-4), mild depression (5-8), moderate depression (9-11), and severe depression (12-15). GDS can be used in mild to moderately cognitively impaired older adults. ISI is a

validated 7-item scale to assess the severity of insomnia. The total score ranges from 0 to 28, with scores of 0-7 indicating no clinically significant insomnia, 8-14 indicating subthreshold insomnia, 15-21 indicating moderate insomnia, and 22-28 indicating severe insomnia. Depressive and sleep symptoms are investigated because elderly people with cognitive impairment often have comorbid emotional and sleep disorders. The benefits of acupuncture and acupressure for depression and insomnia have been confirmed in our previous studies.

(c) Adverse events: The severity of adverse events (AEs) will be assessed according to the Common Terminology Criteria for Adverse Events (CTCAE) v5.0 criteria. AEs will be systematically recorded, in which AEs that first appear in the study or worsen relative to the pre-study status will be recorded at each visit, including the date and time of onset, duration, severity, relationship to intervention, and action taken accordingly. All possible events will be independently evaluated by staff who do not assess treatment outcomes. The causality between treatment procedures and AEs will be assessed.

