Fatal or life-threatening unexpected AEs will be reported to the regulatory bodies as soon as possible but no later than 7 calendar days after first knowledge by the principal investigator (PI) that a case qualifies, followed by as complete a report as possible within 8 additional calendar days. This report would include an assessment of the importance and implications of the findings, including relevant previous experience with the same or similar medicinal products. For other serious, unexpected AEs that are not fatal or life-threatening, they will be reported as soon as possible but no later than 15 calendar days after first knowledge by the PI or that the case meets the minimum criteria for expedited reporting. For non-serious AEs and serious AEs that are expected, they will be reported in a brief summary at the conclusion of the trial.

(d) Assessment schedule: Clinical assessment will be conducted at baseline, week 6, and week 12 (Table 3). For AEs, participants in active treatment groups will be asked whether they have experienced any AEs on each treatment and assessment session. Participants in the control group will be recorded for all AEs on a regular basis (baseline, 6, and 12 weeks).

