(e) Procedures for discontinuation or withdrawal of a subject: The investigator may terminate a subject's study participation at any time during the study when the subject meets the study termination criteria. In addition, a subject may discontinue his or her participation without giving a reason at any time during the study. Should a subject's participation be discontinued, the primary criterion for termination would be recorded. Subjects who discontinue the study during the treatment period will visit the site as soon as possible for clinical assessment, if applicable. To ensure participants' safety, those discontinued because of severe side effects or hospitalizations due to any reason will be given individual clinical treatment. Discontinued or withdrawn subjects will not be replaced.

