- (c) severity of dementia (mild cognitive decline [Stage 3], moderate cognitive decline [Stage 4], moderately severe cognitive decline [Stage 5])

Secondary outcomes

A linear mixed-effect model will be applied to compare the secondary outcomes, including changes in scores of the Digit span test (DSF and DSR), MBI, VAS, GDS and ISI, with time (baseline, week 6, and week 12) and group (CAT, CAE, CAT+CAE, and routine care) as categorical fixed factors and random intercepts within a scaled identity covariance matrix. Gender, age, baseline MoCA score, and baseline medication will serve as covariates.

Pairwise comparisons will be further carried out to examine between-group differences. Two-tailed P-values will be reported in addition to confidence intervals ([Proposed Tables 2 and 3](#)).

Safety outcomes

AEs related to treatment will be tabulated by treatment group without statistical tests or confidence intervals ([Proposed Table 4](#)).

All AEs that occurred throughout the trial will be tabulated by treatment group and AE category (mild, moderate, severe, life-threatening, or death). Chi-square test or Fisher's exact test will be used to detect differences between the four groups ([Proposed Table 5](#)).

Details of serious AEs and death cases will be summarized and listed in a separate table.

Interim analysis

No interim outcome analyses were done prior to the completion of the study to avoid assessment bias.

Missing data

A linear mixed-effect model will be conducted for all analyses of primary and secondary outcomes without imputation of missing data.¹⁶

Proposed Tables

Table 1. Baseline characteristics

Characteristic	CAT (n=62)	CAE (n=62)	CAT+CAE (n=62)	Routine care (n=62)	Total (n=248)	P value
Age, years *	XX ± XX	XX ± XX	XX ± XX	XX ± XX	XX ± XX	XX
Gender (Female) †	XX (XX)	XX (XX)	XX (XX)	XX (XX)	XX (XX)	XX
Marital status †						XX
Married or living with partner	XX (XX)	XX (XX)	XX (XX)	XX (XX)	XX (XX)	
Single, separated, divorced, or widowed	XX (XX)	XX (XX)	XX (XX)	XX (XX)	XX (XX)	
Education level †						XX
Uneducated	XX (XX)	XX (XX)	XX (XX)	XX (XX)	XX (XX)	
Primary or below	XX (XX)	XX (XX)	XX (XX)	XX (XX)	XX (XX)	
Lower Secondary	XX (XX)	XX (XX)	XX (XX)	XX (XX)	XX (XX)	
Upper Secondary	XX (XX)	XX (XX)	XX (XX)	XX (XX)	XX (XX)	
University or above	XX (XX)	XX (XX)	XX (XX)	XX (XX)	XX (XX)	
Past occupation †						XX
Managers and administrators	XX (XX)	XX (XX)	XX (XX)	XX (XX)	XX (XX)	

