‡ P value was calculated using a mixed-effects model with baseline adjustment to illustrate pre- and post-treatment within-group differences. Those which statistical differences $p<0.05$ reached significance level are indicated in bold font

Table 4. Adverse events related to treatment, n (%)^{*}

Adverse event	CAT (n = 62)	CAE (n = 62)	CAT+CAE (n = 62)
Bleeding at the site of needling	XX (XX)	XX (XX)	XX (XX)
Hematoma around the site of needling	XX (XX)	XX (XX)	XX (XX)
Dizziness after treatment	XX (XX)	XX (XX)	XX (XX)
Headache after treatment	XX (XX)	XX (XX)	XX (XX)
Localized pain	XX (XX)	XX (XX)	XX (XX)
Needle phobia	XX (XX)	XX (XX)	XX (XX)

Abbreviations: CAT, comprehensive acupuncture therapy; CAE, Comfy Acupressure for the Elderly.

* Data was expressed as number of patients (%).

Table 5. Reported adverse events in different categories, n (%)^{*}

Adverse Event Category	CAT (n=62)	CAE (n=62)	CAT+CAE (n=62)	Routine care (n=62)	P-value*
Any	XX (XX)	XX (XX)	XX (XX)	XX (XX)	XX
Mild	XX (XX)	XX (XX)	XX (XX)	XX (XX)	XX
Moderate	XX (XX)	XX (XX)	XX (XX)	XX (XX)	XX
Severe	XX (XX)	XX (XX)	XX (XX)	XX (XX)	XX
Life-threatening	XX (XX)	XX (XX)	XX (XX)	XX (XX)	XX
Death	XX (XX)	XX (XX)	XX (XX)	XX (XX)	XX

Abbreviations: CAT, comprehensive acupuncture therapy; CAE, Comfy Acupressure for the Elderly.

* Data was expressed as number of patients (%). Those which statistical differences $p < 0.05$ reached significance level are indicated in bold font.

[figure not shown]

Figure 1. CONSORT Flowchart

References

1. American Psychiatric Pub. Diagnostic and Statistical Manual of Mental Disorders (DSM-5®). American Psychiatric Pub; 2013.

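### Serious adverse events and deaths after early exit but before Week 12 are captured only passively, although SAP Table 5 counts and tests all events over all 62 per arm

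*Protocol*

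**What the plan says.** **Collection.** Under Assessment, item (d), the Protocol states that "participants in active treatment groups will be asked whether they have experienced any AEs on each treatment and assessment session". For routine care it states: "Participants in the control group will be recorded for all AEs on a regular basis (baseline, 6, and 12 weeks"). The visit schedule is "Clinical assessment will be conducted at baseline, week 6, and week 12 (Table 3"), and that table shows no contact after Week 12. Item (c) lists what is recorded for each AE, "including the date and time of onset, duration, severity, relationship to intervention, and action taken accordingly".

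**Exit.** Under Treatment procedure, item (f), participants who cannot tolerate acupuncture or acupressure, or who are hospitalized because their condition worsens, are taken out of the study, not only off treatment. Termination criteria, item (e), then provides: "Subjects who discontinue the study during the treatment period will visit the site as soon as possible for clinical assessment, if applicable". No later AE or vital-status contact is described.

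**Other channels.** Data Management, item (b), gives caregivers emergency telephone numbers for reporting an AE. Assessment, item (c), sets expedited reporting deadlines that run from the time the principal investigator learns of a qualifying event.

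**Analysis.** The SAP, under Safety outcomes, says: "All AEs that occurred throughout the trial will be tabulated by treatment group and AE category (mild, moderate, severe, life-threatening, or death"). It compares the four groups by Chi-square or Fisher's exact test and lists serious AEs and deaths separately. Proposed Table 5, "Reported adverse events in different categories, n" (%), has severe, life-threatening and death rows, each column headed n=62. Neither document says in days or weeks what *throughout the trial* means.

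**The concern.** The scope of the safety analysis is wider than the scope of systematic collection. Suppose a resident is hospitalized in week 7, is discontinued, and dies in hospital in week 9. The death lies inside the 12-week period and belongs in Table 5, but no scheduled contact exists at which it would be recorded.

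The people affected are not a random subset, because being hospitalized or unable to tolerate treatment is what ends their scheduled observation. The rows that matter most for safety are therefore the ones most exposed to missing events, while the denominator stays at 62. Safety is one of the three stated aims of the trial, and Table 5 attaches a P value to each of these rows.

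The undefined period raises a second question. Routine-care participants may choose 12 weeks of active treatment after completing the trial (Treatment procedure, item (e)). Without a stated cut-off, it is unclear whether events during that treatment belong in the routine-care column.

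**Working it through.** **1. Source of the 25%.** The sample-size section gives M = 2.1, SD = 3.6, a constant of 7.9 and 25% dropout.

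- n = 2/(2.1/3.6)² × 7.9 = 46.43
- 46.43/(1 − 0.25) = 61.9, rounded to 62 per arm

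The plan's figure reproduces and is not in dispute. The 25% is used below only as a scale for early exits.

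**2. Number of exits.** 0.25 × 62 = 15.5 per arm; 0.25 × 248 = 62 over four arms.

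**3. Person-time without scheduled safety observation.** Planned time per arm is 62 × 12 = 744 person-weeks. With exits spread evenly over 12 weeks (assumption), the mean time lost is 6 weeks.

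| Mean weeks lost per exit (assumed) | Person-weeks lost | Share of 744 |
|---|---|---|
| 3 (late exits) | 15.5 × 3 = 46.5 | 6.25% |
| 6 (even) | 15.5 × 6 = 93 | 12.5% |
| 9 (early exits) | 15.5 × 9 = 139.5 | 18.75% |

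This is a rough scale. It counts every exit, whatever the reason, and includes exits by death, after which no time is left to observe.

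**4. How often each arm is asked.** CAT is planned as follows: "CAT will be conducted for 2 sessions per week for 12 consecutive weeks, a total of 24 treatment sessions". CAE has 36 sessions, and every arm has two visits after baseline.

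| Arm | Planned AE contacts after baseline, completer | Multiple of routine care |
|---|---|---|
| CAT | 24 + 2 = 26 | 13 |
| CAE | 36 + 2 = 38 | 19 |
| CAT+CAE | up to 24 + 36 + 2 = 62 | up to 31 |
| Routine care | 2 | 1 |

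The CAT+CAE figure is lower if both treatments are given at one attendance. After an exit under Treatment procedure, item (f), the plan leaves one assessment at most in any arm.

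**5. Direction of bias.** Intolerance of treatment can end observation only in the active arms, which could lower their counts. While under treatment, those arms are asked 13 to 31 times as often as routine care, which could raise their counts. Exit after hospitalization applies to all four arms. The documents give no AE or death rates with which to weigh these against each other.

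**The case against.** The strongest reply is that the plan does not rely on visits alone. Caregivers can telephone about any AE, with no end date. Expedited reporting starts from knowledge of the event, not from a visit. Serious AEs and deaths get their own listing without a time limit. The main reason for exit is recorded, so the hospitalization that triggers an exit is not lost. The n=62 denominators follow from the intention-to-treat population, and the 25% is a sample-size allowance, not a forecast of lost safety follow-up.

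All of this is correct, and it rules out several stronger readings that a reader might infer:

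- *AEs are collected only at sessions and visits.* The telephone line and the expedited route contradict this.
- *Nothing is collected after Week 12.* Neither document gives an end date. The schedule merely shows no later contact, and what the analysis covers is undefined.
- *The outcome of unresolved AEs is missing from Table 5.* That table has severity rows only, so apart from death no outcome would appear there under any period. Unresolved AEs affect the duration field instead.
- *Treatment will look safer than it is.* The direction is undetermined, as step 5 of the working shows.

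What the reply does not remove is the gap after exit. The telephone line depends on a caregiver choosing to call about someone already out of the study. The expedited route covers unexpected events and acts once the investigator knows; it does not produce that knowledge. Neither creates a duty to establish whether a discontinued participant was alive at Week 12, or gives comparable ascertainment across the four arms that Table 5 compares.

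**Conclusion.** The point holds as a low-cost improvement to the safety plan, not as an error that invalidates it. After an exit for intolerance or hospitalization, deaths and serious AEs before Week 12 have no scheduled capture beyond one possible assessment, while Table 5 counts and tests them over all 62 per arm.

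At 25% exits spread evenly over 12 weeks, about 12.5% of person-time per arm would lack scheduled safety observation. With mean losses of 3 to 9 weeks per exit, the range is 6.25% to 18.75%. These figures rest on the assumed exit rate and timing. The number of deaths that might be missed cannot be given, because the documents state no mortality rate. No direction of bias should be claimed. Any wish for an additional safety contact after Week 12 is closer to a design preference and is not part of this conclusion.

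**What to change.** **Protocol.** In Treatment procedure (f), Assessment (d) and Termination criteria (e), state that serious AEs and vital status are collected through Week 12 after randomization for every randomized participant, whether or not treatment or visits continue. The source would be the care-home record or the caregiver, within consent, and not where consent to use records has been withdrawn. The ethics text under Data Management already mentions review of clinical records, but does not link it to AEs. This changes data collection only; the rules for stopping treatment are untouched.

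**SAP.** Under Safety outcomes, define *throughout the trial* as randomization to Week 12 in all four arms, and repeat this in a footnote to Table 5. Events during the optional post-trial treatment of routine-care participants then stay out of the routine-care column. For serious or treatment-related AEs still open at exit or at Week 12, complete the duration field with the end date, or mark the event as ongoing at the last date known.

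**Cost.** Wording changes in both documents, plus a record check or call for about 15 to 16 participants per arm (about 62 in total at the 25% allowance) and for open AEs. Recruitment is from nursing and care homes, so the information should be within reach. Reported event counts may rise.
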